## 1. Abbreviations and Definitions of Terms

Abbreviation	Definition
SNF	Skilled nursing facility
ADRD	Alzheimer's disease and related dementias
CTM-15	Care Transitions Measure - 15
PCS	Preparedness for Caregiving scale
BIM	Brief Inventory of Mental Status
EHR	Electronic Health Record
HIPAA	Health Insurance Portability and Accountability Act
RC	Research Coordinator
DEMQOL	Dementia Quality of Life Scale
ED	Emergency department
AE	Adverse event
SAE	Serious adverse event
RN	Registered nurse
SMC	Safety Monitoring Committee
LAR	Legally authorized representative

## 2. PROTOCOL SYNOPSIS

Study Title	Adapting Connect-Home Transitional Care to Fit the Unique Needs of Persons with Alzheimer's Disease and Other Dementias and their Caregivers: A Pilot Study
Funder	National Institute of Nursing Research
Clinical Phase	Phase I
Study Rationale	
The proposed study will examine the feasibility and acceptability of Connect-Home Plus, a transitional care intervention, targeting Skilled Nursing Facility (SNF) patients with Alzheimer's disease and related dementias (ADRD) who discharge to home and their primary caregivers. The study will be set in two North Carolina SNFs and in the patient's home (during intervention periods only). Using a single-arm, post-test-only trial design, SNF patient and caregiver pairs will be enrolled in a study to prepare for discharge to home-based care and implement plans for home-based care after SNF discharge. The study will describe the feasibility and acceptability of Connect-Home Plus and to estimate the impact of Connect-Home Plus on their outcomes in 7 and 30 days.
 
Patients will be identified by consultation with SNF clinical staff and medical record review. After informed consent, baseline enrollment surveys will be collected for patients and caregivers. Additionally, a medical record review for data related to continued health outcomes will be conducted for patients. Telephone questionnaires will be used to survey patients and caregivers at 7, 21, and 60 days after patients return home.

Study Objective(s)	
Primary
 

• Feasibility of the intervention. The feasibility items include: (1) completing the Transition Plan of Care; (2) convening the care plan meeting with caregiver attending; (3) reviewing advance directives in the SNF; (4) scheduling follow-up medical appointments; (5) transmitting records to follow-up clinicians; (6) home care nurse completion of the first home visit within 24 hours after discharge; (7) completion of first caregiver support call within 72 hours of discharge; (8) completion of the second and third caregiver support call within one month of discharge.

• Patient satisfaction with services, including services were easy or difficult to use, supports were or were not helpful, and services helped to manage issues related to ADRD at home.

• Mean caregiver intervention satisfaction scores, including services were easy or difficult to use, supports were or were not helpful, and services helped to manage issues related to ADRD at home.

 
Secondary

- 
- Patient preparedness for discharge will be measured by the Care Transitions Measure-15 (CTM-15), which measures self-reported knowledge and skills for continuing care at home.
  - Caregiver preparedness for caregiving will be measured by the Preparedness for Caregiving Scale (PCS), which measures self-reported readiness for caregiving.
  - Patient function will be measured using the Life Space Assessment, where scores are the product of the "Life-space level" (range 1-5) and the "independence" score (range 1-2).
  - The quality of life of the patient will be assessed with the Dementia Quality of Life Measure.
  - When the patient is unable to rate their quality of life, the quality of life will be rated by their caregiver, using the Dementia Quality of Life-Proxy measure.
  - Patient-reported Days of Emergency Department or Hospital Use 30 Days After Skilled Nursing Facility Discharge.
  - Caregiver burden will be measured using the Zarit Caregiver Burden Scale, measuring caregiver perceptions that "caregiving has an adverse effect on their emotional, social, financial, physical and spiritual functioning."
  - Caregiver distress will be measured using the Distress Thermometer.
- 

**Test Article(s)  
(If Applicable)**

Connect-Home Plus is a two-step transitional care intervention: 1) SNF staff create an individualized Transition Plan or Care and prepare the patient with ADRD and caregiver to manage the patient's illness at home; and 2) within 3 days of discharge a home care nurse visits the patient and caregiver at home and within 30 days of SNF discharge, a dementia caregiving specialist calls the caregiver at home and helps them implement the written Transition Plan of Care. Both intervention steps focus on 6 key care needs to optimize patient and caregiver outcomes: 1) home safety and level of assistance; 2) advance care planning; 3) symptom management; 4) medication reconciliation; 5) function.

---

**Study Design**

The study will use a single-arm, post-test-only trial design to examine the feasibility and acceptability of the intervention and estimate of patient and caregiver outcomes in 7 and 30 days after SNF discharge.

---

**Subject Population**

**key criteria for Inclusion and Exclusion:**

**Patient Inclusion Criteria:**

- be able to speak English
  - have a goal of discharge to home
  - have a diagnosis of ADRD, or a Brief Inventory of Mental Status (BIMS) score <13, or (for persons unable to complete the BIMS assessment), have a Cognitive performance score of  $\geq 3$  (calculated using data in the Minimum Data Set 3.0 and an algorithm for estimating cognitive impairment using Minimum Data Set 3.0 data other than BIMS)
  - have a caregiver willing to participate.
  - for patients with documentation in the medical record of a caregiver who is the patient's legally authorized representative,
-

consent of the caregiver to participate in the study as the patient's representative.

**Patient Exclusion Criteria:**

- be unable to speak English

**Caregiver Inclusion Criteria**

- self-report assisting the patient at home
- be able to speak English.

**Caregiver Exclusion Criteria**

- be unable to speak English

---

Number Of Subjects	20 persons with ADRD and their 20 caregivers in 2 SNFs
---------------------------	--

---

Study Duration	Participants will be recruited during the SNF stay, when baseline data will be collected, and they will participate in the study for up to 60 days post-discharge. The entire study is expected to last 6 months.
-----------------------	---

---

Study Phases	The study team will use a limited waiver of HIPAA authorization to pre-screening for patient and caregiver eligibility during the SNF admission. The study team will recruit SNF patients and their caregivers in-person (or, when risk mitigation related to COVID-19 prevents in-person contact, we will recruit virtually, using an iPad and connection via ZOOM) within 10 days of their admission and will review the patient's medical record to confirm eligibility. The study team will obtain written consent (or, when risk mitigation related to COVID-19 prevents in-person contact, they will obtain verbal consent) of SNF patients and their caregivers. The study team will collect baseline data during the SNF admission. SNF patients and caregivers will receive the Connect-Home Plus intervention in the SNF and the SNF caregivers will receive the intervention after the SNF discharge in a home visit with the home care nurse and in telephone calls with the dementia caregiving specialist in 30 days after SNF discharge. The study team will collect outcome data from the patient and caregiver (or from the caregiver only if the patient is not able to participate in data collection) in 7, 21, and 30 days after SNF discharge. The chart review of medical records will occur in 30 days after SNF discharge.
---------------------	---

---

Efficacy Evaluations	The study will not generate efficacy data. The primary outcome evaluation will use descriptive statistics to describe feasibility and acceptability of Connect-Home Plus.
-----------------------------	--

---

Pharmacokinetic Evaluations	n/a
------------------------------------	-----

---

Safety Evaluations	Study progress and safety will be reviewed monthly (and more frequently if needed). Progress reports will include patient and caregiver recruitment, retention/attrition, and adverse events. In addition, safety evaluation will include (1) whether adverse event rates are consistent with pre-study assumptions; (2) reason for dropouts from the study; (3) whether all participants met entry criteria; (4) whether continuation of the study is justified on the basis that additional data are needed to accomplish the stated aims of the study; and (5) conditions whereby the study might be terminated prematurely.
---------------------------	---

---

Statistical And Analytic Plan	
Descriptive statistics will be used to describe the feasibility of the intervention.
 
Descriptive statistics will be used to describe the acceptability of Connect-Home Plus to patients and caregivers. De-identified, exemplar patient or caregiver statements will be identified to illustrate trends in the satisfaction survey responses.
 
Descriptive statistics will be used to describe secondary outcomes, including patient and caregiver reported preparedness for care after discharge; patient quality of life and patient functional mobility; caregiver burden and distress; and patient use of hospital and ED services after discharge.

DATA AND SAFETY MONITORING PLAN	
This study will require a Data Safety Monitoring Committee and Plan. An Executive Committee and Adverse Event Monitoring Committee will be created to assure that the study meets expectations and any risk to participants are reduced to a minimum. These committees will meet on a regular basis as laid out in the Data Safety and Monitoring Plan

---

### 3. BACKGROUND AND RATIONALE

#### Introduction

The study setting is two SNFs that participated in earlier Connect-Home pilot studies (2014-2018) and have sustained Connect-Home implementation to date.(1) The pilot-test of Connect-Home Plus will be in the SNFs and the homes of the caregivers of patients with ADRD, where a community-based, dementia caregiving specialist will call the caregiver after SNF discharge.

The rationale for the study is to determine the feasibility and acceptability of the Connect-Home Plus intervention that is designed to promote successful transitions of care of SNF patients with ADRD and their caregivers during transitions from SNF to home.

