This study will build on findings in an ongoing clinical trial of the Connect-Home intervention, which tests a transitional care intervention with high potential for adapting to the unique needs of persons with ADRD and caregivers.(19) The objective of the Connect-Home trial (ongoing) is to conduct a stepped-wedge cluster-randomized trial to test Connect-Home transitional care against standard discharge planning (control) using individuals discharged to home (N=360) and their caregivers (N=360) in 6 SNFs. The Specific Aims are to evaluate the efficacy of Connect-Home to improve: (1) SNF patient and caregiver preparedness for discharge (primary outcome, assessed 7 days after discharge), (2) patient quality of life, function, and acute care use, and (3) caregiver burden and distress (secondary outcomes assessed 30 and 60 days after discharge home). The setting is six SNFs and, for participants in the intervention arm, patient homes, where community-based RNs visit them within 24 hours of discharge. The Connect-Home Intervention involves new organizational structure, including: (1) the “Transition Plan of Care Template,” installed in the SNF EHR system, which staff use to record transitional care goals and deliver the intervention; (2) the “Connect-Home Toolkit,” a manual with standard procedures and tools; and (3) staff training to deliver transitional care processes that address key care needs of SNF patients and their caregiver. Connect-Home structures support transitional care processes in the SNF and the person’s home. In collaboration with the SNF patient and their caregiver, SNF nurses, social workers and

rehabilitation therapists (1) set goals for home-based care, (2) make plans for transition from SNF to home, and (3) make preparations for home-based care (e.g., teach symptom management). Following discharge, community-based RNs implement the transition plan (e.g., set-up new routines for self-care at home).(19) In the proposed study, Connect-Home structure and processes provide a robust foundation for adapting transitional care for persons with ADRD and their caregivers.

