The study, described in this protocol, builds on a completed, systematic adaptation of Connect-Home to align with the Alzheimer's Association "Practice Recommendations for Person-Centered Care" and address unmet care needs of persons with ADRD.(20) Numerous frameworks describe adaptation as a systematic progression using steps required to modify an intervention to fit the needs of new populations or contexts and ensure acceptability to key stakeholders.(21) A central goal of adaptation is to modify the form of the intervention (i.e., structure), while maintaining fidelity to its underlying program theory.(21) Consistent with this goal, we modified Connect-Home structures (plan of care template, toolkit, training) while retaining the underlying program theory. We modified structures with the goal of building staff capacity to tailor the existing set of six Connect-Home transitional care processes to the distinct needs of persons with ADRD and their caregivers. In doing so we retained fidelity to the program theory, which hypothesizes that the six key processes are the causal mechanisms through which Connect-Home improves patient and caregiver outcomes.(1, 22) Thus, for example, the adaptation of Connect-Home added elements to the EHR template for the Transition Plan of Care (structure) to prompt for staff to tailor coordination of medical care (key process) to include needed referrals for dementia follow-up care.(16, 23) Another adaptation was to modify the Connect-Home training protocol (structure) and add staff training content on tailoring care plans for symptom management (key process), with guidance for needed home-based care of neuropsychiatric symptoms such as withdrawal, agitation, and resistance to care. Our approach to adaptation followed the five steps described by Chen et al. (2013).(24) This included: learning from staff in SNFs with four years of experience using the un-adapted version of Connect-Home, convening a steering committee, determining the fit of Connect-Home with the transitional care needs of persons with ADRD and their caregivers, summarizing findings and create a list of unmet needs, and making choices about how to adapt Connect-Home to address unmet needs.

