#### 4. STUDY OBJECTIVES

the objective of this study is to test the feasibility and acceptability of the adapted intervention (Connect-Home Plus) in a total sample of 20 patients and 20 caregivers in two SNFs.

**Primary Objective:** Determine the feasibility and acceptability of the adapted version of Connect-Home.

**Secondary Objective:** Determine estimated mean outcomes of persons with ADRD and their caregivers, e.g., preparedness for discharge, quality of life, hospital readmission, and caregiver burden).

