#### Outcome Measures

- Primary Outcome Measures:

- Number of participants for whom the intervention components were feasible. Feasibility will be measured using an instrument to audit skilled nursing facility medical records of the patient and the intervention log of services for the patient.(1) It includes eight dichotomous (yes-no) items that indicate feasibility of the Connect-Home Plus intervention. The feasibility items include: (1) completing the Transition Plan of Care; (2) convening the care plan meeting with caregiver attending; (3) reviewing advance directives in the SNF; (4) scheduling follow-up medical appointments; (5) transmitting records to follow-up clinicians; (6) home care nurse completion of the first home visit within 24 hours after discharge; (7) completion of first caregiver support call within 72 hours of discharge; (8) completion of the second and third caregiver support call within one month of discharge. A "Yes" answer indicates that the intervention component was feasible to provide for the patient and caregiver dyad.
- Mean patient intervention satisfaction scores. This interview guide will be used to assess the acceptability of Connect-Home Plus with persons with ADRD. The interview will include questions about (1) factors that made the Connect-Home Plus transitional care services easy or difficult to use, (2) specific supports that were and were not helpful, (3) the effect of Connect-Home Plus on how to manage issues related to ADRD at home, and (4) unmet needs for care of issues related to ADRD at home.(1) Responses to the interview guide questions will be used to generate 3 4-point Likert scale acceptability scores, including (how helpful was Connect-Home Plus, (2) how difficult were these services to use, and (3) how well did these services prepare you for care at home. The scores will include 0 meaning not applicable, and scores 1-3 indicating acceptability, with lower scores indicating higher acceptability.

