Staff Training	
Site Leadership Training (1 hour). PI trains 1-2 SNF project leaders. Content: the Connect-Home Plus protocol and study procedures.
 
Staff Training (2 hours) In each SNF, the SNF staff were previously trained with the Connect-Home protocol. Thus, staff training with the Connect-Home Plus protocol will be two hours (as opposed to 4 hours in the parent study), with a special focus on services to care for persons with ADRD and their caregivers. The PI will train social workers, nurses, rehabilitation therapists. Training content: 1) Patient and caregiver key care needs (home safety and level of assistance, advance care planning, symptom management, medication reconciliation, function and activity, and coordination of follow-up medical care). 2) Protocols for using the two-step intervention to address patients’ key care needs and unique needs of persons living with dementia and their caregivers. 3) Using the EHR template to individualize patients’ Transition Plan of Care. 4) Advance care planning (identify surrogate, Health Care Power of Attorney, existing advance directives). 5) Integrating SNF-based and home-based care (e.g., clinical hand-offs from SNF to home care RNs, the dementia caregiver specialist, and follow-up medical providers). Teaching Strategy: Presentation, the Connect-Home Plus Toolkit and teach-back.
 
Focused Training for Home Care RNs (1.5 hours). The PI will provide additional training for home care RNs in up to 3 home care agencies that will participate in the pilot study (Table 2, below). Training content: The importance of home care follow-up within 24 hours of discharge, strategies for implementing the Transition Plans of Care, key care needs of persons living with ADRD and their caregivers and responding to medical needs. Teaching strategy: Presentation, the Connect-Home Plus Toolkit and teach-back.
 
Focused Training for Dementia Caregiver Specialist (2 hours). The PI will train an occupational therapist to serve in the role of dementia caregiver specialist. Training content: 1) the Connect-Home schedule of care, 2) the Transition Plan of Care, 3) key care needs of persons living with ADRD and their caregivers, 4) the post-discharge call back script, 5) procedures for communication with the SNF staff, and 6) procedures for maintaining a record of call backs using the Call-
 
New Staff Training (1-2 hours, as needed): The PI trains replacement staff to use the Connect-Home Plus protocol.

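### None of feasibility items 1–6 checks ADRD-specific content, so good results on them, or even on all eight items, would not show that the adaptation was delivered in the SNF or at the home visit

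*Combined protocol and SAP*

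**What the plan says.** Section 4 gives the primary objective: "Determine the feasibility and acceptability of the adapted version of Connect-Home". Section 8 (Primary Endpoint) equates feasibility with staff delivering the Connect-Home Plus components the way they were designed.

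Section 7 (Outcome Measures) defines the audit: "It includes eight dichotomous (yes-no) items that indicate feasibility of the Connect-Home Plus intervention". The list opens with "1) completing the Transition Plan of Care; (2) convening the care plan meeting with caregiver attending". It continues with advance directives, follow-up appointments, record transfer, a first nurse visit within 24 hours, and two items on caregiver calls. A positive reply is explained as follows: "answer indicates that the intervention component was feasible to provide for the patient and caregiver dyad".

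On the sites, the Introduction in Section 3 says they "have sustained Connect-Home implementation to date", and Table 4 in Section 9 adds: "In each SNF, the SNF staff were previously trained with the Connect-Home protocol". Un-adapted Connect-Home already had a Transition Plan template, described under Relevant Literature and Data as "installed in the SNF EHR system, which staff use to record transitional care goals and deliver the intervention".

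The same section says that the adaptation changed the template, toolkit and training and kept the six existing care processes. Its example is a template change that prompts staff to tailor coordination of medical care "to include needed referrals for dementia follow-up care". Table 5 places further ADRD content in Step 1: goals tailored to ADRD, and discussion of the patient's cognitive impairment or diagnosis at the planning meeting. Table 4 adds ADRD care needs to the home care nurses' training.

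**The concern.** Apart from the specialist's calls, the new part of Connect-Home Plus is content placed inside familiar steps. The audit records that the steps happened. As the items are worded, a plan with no ADRD content, or a meeting that never touched on cognition, earns the same Yes as a fully tailored one. The sites have years of practice with the parent intervention, so good results on items 1–6 may reflect existing routine.

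The result has a use. Under Potential Benefits, Section 3 says that a feasible and acceptable outcome will supply the rationale for an efficacy trial. That trial could begin with no record of whether SNF staff and home care nurses can deliver the ADRD tailoring.

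**Working it through.** The plan gives no feasibility threshold, summary score or sample-size formula, so it has no figure to reproduce. The check is a mapping of the items, followed by a comparison of scenarios.

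**Step 1: map the items.**

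| Item | Counterpart in un-adapted Connect-Home | Asks for ADRD content? |
|---|---|---|
| 1 Transition Plan | Explicit: template described in Section 3; earlier version installed at both sites (Table 4). The pilot uses a modified template. | No |
| 2 Care plan meeting | Inferred: Section 3 describes transition planning with patient and caregiver | No |
| 3 Advance directives | Inferred: six processes retained (Section 3); advance care planning is among the care needs in Table 4 | No |
| 4 Appointments | Inferred: coordination of medical care is named as a key process (Section 3) | No |
| 5 Records sent | Inferred, as for item 4 | No |
| 6 Nurse visit in 24 h | Described for the ongoing six-SNF trial; not shown for these two sites; delivered by home care agencies (Table 4) | No |
| 7–8 Caregiver calls | None: described as part of Connect-Home Plus (Section 7) | New component, made by study staff |

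**Step 2: count.**
- Items 1–6, with no ADRD content check: 6/8 = 75%, or 6 × 20 = 120 of 8 × 20 = 160 item checks over 20 dyads.
- Items delivered inside the SNF (1–5): 5/8 = 62.5%, or 100 of 160.
- Items capturing a new component (7–8): 2/8 = 25%.
- Items checking ADRD tailoring in Step 1 or at the home visit: 0/8.

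**Step 3: compare three scenarios, n = 20.** Assume that the ordinary steps are always completed and are scored as the items are worded. Exact (Clopper–Pearson) 95% limits: for 20/20 the lower limit is 0.025^(1/20) = 83.2%; for 0/20 the upper limit is 1 − 0.025^(1/20) = 16.8%.

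| Scenario | Each of items 1–6 | Each of items 7–8 |
|---|---|---|
| A. Steps, tailoring and calls all delivered | 20/20 (83.2–100%) | 20/20 (83.2–100%) |
| B. Steps and calls delivered, no tailoring | 20/20 (83.2–100%) | 20/20 (83.2–100%) |
| C. Steps only: no tailoring, no calls | 20/20 (83.2–100%) | 0/20 (0–16.8%) |

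The audit separates C from A, because results are described by component. It cannot separate B from A, and no choice of summary changes that.

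**Step 4: look for the information elsewhere.** The chart variables in Section 7 include cognitive status but nothing on ADRD content in the care plan. The specialist's log records what each call covered; nothing similar exists for Step 1 or the home visit. The satisfaction interviews raise ADRD issues, but the three scores drawn from them concern helpfulness, difficulty of use and preparation for home. Those are perceptions, not records of delivery.

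**The case against.** Several counter-arguments limit the point.

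- **Items 1–6 belong in the audit.** The adaptation deliberately keeps the six processes. Whether staff can still complete these steps in an all-ADRD sample, with more to cover, is a fair feasibility question. This stands, and is why the items should stay.
- **Prior use is only partly documented.** A reader might infer that both SNFs already carry out six of the eight audited steps. The protocol supports this for Connect-Home as a whole and for the template. Items 2–5 are inference. For item 6, the 24-hour visit is described for another trial, and nothing says that these two sites' patients already receive it.
- **Earlier feasibility findings.** A reader might infer that items 1–6 were already shown to be feasible. In Sections 3 and 9 that statement refers to the template, toolkit and training, not to the audited steps.
- **A false claim of success.** A reader might infer that the primary outcome could look high with nothing new delivered. The plan has no summed score or threshold, missed calls would show on items 7–8, and two satisfaction outcomes are also primary. If someone did average the items in scenario C, the result would be 6/8 = 75%; a rule requiring all eight would give 0%.
- **Scoring rules are not shown.** The audit guide is not reproduced in the protocol. It may say what counts as a completed plan. The point therefore rests on the items as worded.

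None of these closes the gap between scenarios A and B.

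**Conclusion.** The concern holds in a limited form. None of items 1–6 asks for ADRD content. Only 2 of 8 items capture a new component, and 0 of 8 check the tailoring in Step 1 or at the home visit. High results on items 1–6, or 8/8 when study staff make the calls, are therefore not evidence that the tailoring was delivered as designed.

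This rests on two assumptions: that the audit guide scores the items as Section 7 words them, and that items 2–5 resemble what the sites already do. The second affects only how far existing routine could explain good results; the missing content check does not depend on it.

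The documents do not support the stronger conclusion that the study would declare the adaptation feasible on evidence about the old intervention, because they set no decision rule. This is a worthwhile, inexpensive improvement to a descriptive pilot, and it does not invalidate the design.

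**What to change.** Keep the eight items unchanged, so that they stay comparable with the earlier work. Add four lines to the chart audit, each scored yes, no or not applicable:

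- (a) ADRD-tailored goals are recorded in the adapted Transition Plan;
- (b) dementia follow-up referral was addressed, where needed;
- (c) guidance on neuropsychiatric symptoms is recorded, where such symptoms are present;
- (d) cognitive impairment or the dementia diagnosis was discussed at the care plan meeting.

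The not-applicable option matters for (b) and (c): Section 3 speaks of referrals that are needed, and not every patient will have neuropsychiatric symptoms. Report the number assessable beside each result.

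In Section 8, report items 1–6, items 7–8 and the ADRD-content lines as three separate groups. State that any conclusion that the adaptation is feasible must also draw on the last two groups.

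Cost: 4 × 20 = 80 extra checks, beside the 160 already planned, in an audit the research coordinator already performs. Table 4 describes the template as free text in six domains, so a short written scoring rule is needed before the first chart is read. These lines cover mainly Step 1; tailoring at the home visit would stay unaudited unless visit records are available, and the report should say so.
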